In many current studies of peanut OIT, subjects are initially desensitized and then subsequently asked to avoid peanut for a discrete amount of time in order to assess the durability of the desensitization effect (sustained unresponsiveness). This research is critical to understanding the clinical and immunologic changes induced by peanut OIT and longer term implications of therapy. However, in the course of these investigations, the potential exists for subjects to lose their desensitization to peanut and their protection against accidental exposures to peanut.

The majority of current studies of OIT utilize a placebo group, some for extended periods of time (> 1 year). These extended placebo courses are vital to understanding the efficacy of OIT as up to 20% of peanut-allergic patients are thought to naturally develop tolerance to peanut. These subjects are not thought to be at any higher risk than those who are strictly avoiding peanut which is the current standard of care. However, concerns remain with withholding potentially protective treatment for these extended periods of time.

The use of investigational drugs to induce and maintain desensitization has been and continues to be the subject of numerous ongoing studies. However, there has been growing interest in the use of food products to maintain this effect with the thought that these readily available foods may allow for superior compliance. The safety and compliance with transitioning to a non-drug equivalent amount of peanut food has not been well studied.

The goals of this study protocol are several-fold. First and foremost, we would like to provide a salvage therapy option for those previously involved in vital peanut allergy research. Simultaneously, we will address three research aims:

Aim 1 --Investigate the safety and compliance in the 2-stage protocol in subjects who either (a) have previously developed desensitization and then subsequently lost this protection due to a period of time off of therapy or (b) have previously endured an extended time on placebo therapy.

Aim 2 -- Characterize and compare the two stages of the protocol in terms of safety and compliance.

Aim 3 -- Explore the mechanisms responsible for long-term desensitization and/or tolerance to food allergens induced by immunotherapy.

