In doing this, we aim to add to the accumulating pool of data on the safety of OIT while providing a salvage option for these subjects. The data generated from our study can guide future research to identify high risk groups for peanut oral immunotherapy, and compare safety and compliance between peanut OIT and peanut food equivalents. A food equivalent of peanut containing food is an available food in the market with known doses of peanut protein (e.g. Reese's peanut butter cups, Peanut M&Ms, etc.)

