5. STUDY DESIGN AND SCHEDULE

A. LOCATION

Visits will be done at the University of North Carolina-Chapel Hill Food Allergy Study Center (FASC), located in the CTRC building. The FASC is equipped as a clinic. In addition to MD and NP coverage, there are 24-hour adult and pediatric rapid response teams in case of emergencies. The study

site is adjacent to the UNC Hospitals Emergency Department where subjects can be transferred for continued monitoring and acute care as needed.

B. DURATION OF ENROLLMENT

The study enrollment duration is for 2 years or until a commercial peanut OIT products is available to participants whichever is sooner.

C. DURATION OF THE STUDY PER PARTICIPANT

Each participant will be in the study for a total of 12 months. There will be three phases in the study: escalation phase for 1 day, build up phase up to 16 weeks, and maintenance phase up to 3 months on peanut OIT followed by 6 months of food equivalent to tolerated peanut protein.

D. STUDY VISITS

Participants will have: an initial study visit (screening), followed by one visit for the escalation phase, followed by visits every 1-2 weeks for the up dosing phase, a visit at the end of peanut OIT treatment at 6 months, a phone interview at 9 months and a final visit at the end of the study at 12 months. The screening visit may be combined with the initial escalation visit.

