3. BUILD UP PHASE

After the first day of desensitization, subjects will return to the research unit the following day to begin the build-up phase of the study. The subject will ingest 6 mg, or a lower amount based on the reaction during the escalation phase. After the subject is observed for a minimum of 30 minutes for symptoms to the study protein ingestion, he or she will be discharged from the research unit and will continue to consume the study protein at home daily fourteen days (-3/+7 days). The family receives the study protein doses as a powder that they give to the child each day by sprinkling it on a previously tolerated food (e.g., apple sauce). Subsequently, subjects will return to the clinical research unit every 2 weeks (-3/+7 days) to monitor their adherence to the dosage administration and increase the dose to the next escalation amount (Table II). Vital signs are performed prior to the dose administration, prior to the completion of the observation period before discharge, and anytime symptoms occur. If the study team feels that a longer observation time is warranted based on the prior dosing history of the subject or their current physical status, the subject will be observed for a longer period of time. If symptoms occur that do not require treatment, the subject will

be observed until they resolve. If symptoms occur that require diphenhydramine or albuterol, the subject will be observed a minimum of 2 hours or until symptoms resolve. If symptoms occur that require epinephrine, the subject will be observed at least 4 hours or until symptoms resolve. If symptoms do not fully resolve after 6 hours or if new symptoms occur, the subject will be transferred to UNC Children's Hospital to be observed overnight. Per individual stopping rules, participants experiencing severe symptoms during buildup will be terminated from the study.

Subjects who tolerate dose escalations will take that dose daily for a period 2 weeks (-3/+7 days) after which they will return to the clinical research unit to have the daily dose increased proportionately at each visit until the maximum daily dose of study protein (300 mg) is reached. Mechanistic studies may be done at the discretion of investigator to address any clinical symptoms for further studies.

Table II

Dose #	Dose	Interval(weeks)
5	6mg	Day 2
6	12mg	2
7	25mg	2
8	50mg	2
9	75mg	2
10	100mg	2
11	150mg	2
12	225mg	2
13	300mg	2

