4. MAINTENANCE PHASE

After completing build up phase to 300 mg study protein, the subjects will continue to receive their maintenance dose of study protein daily for the proceeding 3 months of the study (maintenance phase). After 3 months of maintenance, the subject may have mechanistic studies done at end of study visit. Data from our previous studies indicate that home dosing is safe, with infrequent

reactions which are typically mild. These data have identified several risk factors for reactions, which include dosing on an empty stomach, fever/illness, and activity/exercise shortly before or after dosing. Families of subjects will be asked to administer the study protein with additional food such as at snack or meal times, and will be instructed to hold the dose during illness and contact study personnel for instruction. After 3 months of daily maintenance peanut protein OIT, subjects will have a follow up visit where they are assessed by study investigator and if qualified they will be switched to food equivalent of peanut protein for the following 6 months.

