5. PEANUT FOOD EQUIVALENT PHASE

At the end of maintenance peanut OIT phase, subjects will be given instruction during their last study visit in maintenance phase to start a peanut food equivalent of 300 mg peanut protein: which include the following options: peanuts (not dry roasted), peanut butter, powdered peanut butter, mini snickers, mini Reese's cup, cheese peanut butter crackers, Reese's pieces, Reese's peanut butter chips or Goober. An instruction sheet will be provided on how much to take of one of these products on a daily basis. This phase will last for 6 months. During this phase, subjects will continue to fill compliance sheets and they will receive phone calls from study coordinators at 9 months. This will be no study visits until the end of this phase to hand daily compliance sheets and fill a survey. At the end of the study the subjects may have the option to enroll in our peanut OIT follow up study if study investigator deemed they meet inclusion criteria for the study.

E. HANDLING ADVERSE REACTIONS AND FOLLOW UP DURING HOME DOSING

Each subject is given multiple ways to contact study staff when they are enrolled in the study. This is reviewed at the end of each visit. The families are told to contact the study staff if they have any questions or concerns before the next visit or at any time during the study. Study contact information given to families include the research clinic phone number, email addresses and office numbers of the, study coordinators, and instructions for how to get in contact with the pediatric on-call allergist who can reach the lead coordinator if needed. Subjects who have any symptoms during observed dosing, or those who express any specific concerns are given a follow up phone call on the day after dose escalation. All subjects will be asked to carry an auto-injector epinephrine. If prescription is not provided by their physician, we will provide them with a prescription for an auto-injector epinephrine. We will ask subjects to fill their prescription and

bring their epinephrine auto-injector with them before starting treatment to verify they have filled their prescription.

F. MANAGING MISSED DOSES

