Aim 2. Characterize and compare the two stages of the protocol in terms of safety and compliance.

We will rely on the following methods to accomplish Aim 2:

1. Our main analyses will focus on stage-specific estimates of incidence rates of adverse events and the proportion of days of treatment missed.

Comparisons of the two stages will rely on logistic regression models for rates, and generalized log-linear models for counts of days. The primary emphasis will be on point estimates and confidence interval estimates. No hypothesis tests will be performed.

2. Our secondary analyses will include estimation of

- the stage-specific incidence rates of gastrointestinal AEs during the entire 2-stage treatment sequence.
- the stage-specific incidence rates of Epipen use
- the stage-specific incidence rates of drop-outs due to gastrointestinal AEs.

Comparisons of the two stages will rely on logistic regression models for rates, and generalized log-linear models for counts of Epipen usages. The primary emphasis will be on point estimates and confidence interval estimates. No hypothesis tests will be performed.

3. Exploratory analyses will be used to investigate potential candidate risk factors for AEs (using logistic regression models) and causes of missed treatment days (using generalized log-linear models for counts of days).

4. Descriptive tabular and graphical methods will be used to visualize the data and examine the relationships among the measures of interest using graphical and descriptive methods.

Statistical estimates of interest include stage-specific parameter estimates (e.g., incidence rates) as well as estimates of differences between stage-specific parameters (e.g., odds ratios, or rate differences). All statistical estimates will be tabulated with the corresponding 95% confidence intervals (CI). Interpretation of these CIs will be an integral part of analysis. For Aim 2, sensitivity analyses will be performed to evaluate the robustness of the main

results to reasonable perturbations of the choices of statistical methods and statistical assumptions used.

Aim 3. Explore the mechanisms responsible for long-term desensitization and/or tolerance to food allergens induced by immunotherapy.

We will rely on the following methods to accomplish Aim 3:

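### Aim 2 compares the 300 mg food stage only with the whole OIT stage, so the contrast describes the stages but cannot be read as flour against food

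*Combined protocol and SAP*

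**What the plan says.** The synopsis defines two stages: peanut OIT, then extended maintenance on a food equivalent. Section 5.C divides the first into "escalation phase for 1 day, build up phase up to 16 weeks, and maintenance phase up to 3 months on peanut OIT". Table II (section 5.D.3) takes the daily dose from 6 mg to 300 mg in eight increases at two-week intervals. Section 5.D gives visits as "followed by visits every 1-2 weeks for the up dosing phase, a visit at the end of peanut OIT treatment at 6 months". Section 7.E limits flour to 6 months in total. In section 5.D.5, participants are told "to start a peanut food equivalent of 300 mg peanut protein", taken daily for 6 months, with a phone call at 9 months and no visit until the end.

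Entry to the food stage is conditional. Section 5.D.3 says that "participants experiencing severe symptoms during buildup will be terminated from the study". Section 4.C also allows withdrawal for severe symptoms in maintenance. Section 5.D.4 says of those who complete maintenance that "if qualified they will be switched to food equivalent of peanut protein for the following 6 months". Section 10.A keeps withdrawn participants in the analyses.

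For Aim 2, section 10.B states: "Our main analyses will focus on stage-specific estimates of incidence rates of adverse events and the proportion of days of treatment missed". It sets stage against stage for AEs, missed days, gastrointestinal AEs, Epipen use and gastrointestinal drop-outs. It uses logistic and log-linear models, reports 95% confidence intervals and performs no tests. No section splits OIT by phase for analysis, names a phase term, or sets a contrast at equal dose.

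On motivation, section 1.B says: "The safety and compliance with transitioning to a non-drug equivalent amount of peanut food has not been well studied". It adds that the data can guide future research and "compare safety and compliance between peanut OIT and peanut food equivalents".

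**The concern.** A reader of the Aim 2 results will want to know whether moving from flour to ordinary peanut food changes safety or adherence. The planned contrast brings in three other differences:

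- **Dosing phase.** Build-up, with its eight dose increases, lies wholly on the OIT side.
- **Early termination.** A participant terminated in build-up counts in the OIT stage and never in the food stage.
- **Ascertainment.** Section 8.D lists questioning at visits as one way AEs are found. Visits come every 1-2 weeks in build-up. The food stage has one phone call and a final visit. Compliance sheets that record reactions run in both stages (sections 5.D.5 and 6.F), so the difference is one of degree.

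If build-up has more recorded AEs than maintenance, food could look no worse than flour, or better, while being worse at the same dose. If build-up has fewer, food would look worse than it is. The harm is to interpretation of Aim 2: no test, primary outcome or stopping rule depends on this contrast.

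**Working it through.** **Inputs from the documents.** Two-week build-up: 8 × 14 = 112 days, which reproduces the 16 weeks in section 5.C. Weekly build-up, the short end of the visit interval in section 5.D: 8 × 7 = 56 days. Maintenance: 3 months, taken as 91 days, or 182 − 112 = 70 days if two-week steps must fit the 6-month limit in section 7.E. Food: 182 days. The single escalation day is ignored.

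**Share of flour time below 300 mg.** Two-week steps: 112/203 = 55%. Two-week steps, capped: 112/182 = 62%. Weekly steps: 56/147 = 38%.

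**Effect on the AE rate ratio.** The documents give no AE rates, so every rate here is an assumption. Set the flour maintenance rate to 1, the build-up rate to b and the food rate to 1.5. With D build-up days and M maintenance days, the whole-stage ratio of food to OIT is 1.5 × (D + M)/(D × b + M).

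| Schedule (D, M) | b = 0.5 | b = 1 | b = 1.5 | b = 2 | b = 3 | b at which ratio = 1 |
|---|---|---|---|---|---|---|
| Two-week steps (112, 91) | 2.07 | 1.50 | 1.18 | 0.97 | 0.71 | 1.91 |
| Two-week steps, capped (112, 70) | 2.17 | 1.50 | 1.15 | 0.93 | 0.67 | 1.81 |
| Weekly steps (56, 91) | 1.85 | 1.50 | 1.26 | 1.09 | 0.85 | 2.31 |

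The last column is (1.5 × (D + M) − M)/D. At b = 1 there is no distortion. At b = 2 the ratio falls below 1 on the two-week schedules but not on the weekly one.

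With no product difference, replace 1.5 by 1. At b = 2 the ratio is 203/315 = 0.64 (two-week steps) or 147/203 = 0.72 (weekly steps). At b = 0.5 it is 203/147 = 1.38 or 147/119 = 1.24.

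**Early termination alone.** Assume 100 participants, no product effect, and a 40% risk of any AE in each stage for those not terminated. All those terminated in build-up have an AE.

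- 3 terminated: OIT 41.8/100, food 38.8/97, odds ratio 0.93.
- 5 terminated: OIT 43/100, food 38/95, odds ratio 0.88.
- 10 terminated: OIT 46/100, food 36/90, odds ratio 0.78.

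Three is a useful reference. Section 4.D suspends enrolment and build-up after more than 3 related severe events other than anaphylaxis (pooled with eosinophilic esophagitis). Anaphylaxis is exempt, so larger numbers are possible.

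**Whether a maintenance contrast among switchers is unbiased.** It is not. Take 100 participants in 300 mg maintenance, 40 with an AE, no product effect and a 40% AE risk on food. If 5 of the 40 are withdrawn, switchers show 35/95 in maintenance and 38/95 on food, odds ratio 1.14. If 10 are withdrawn, it is 30/90 against 36/90, odds ratio 1.33. Using everyone who enters maintenance gives 40/100 against 38/95 in the first case, odds ratio 1.00. If those withdrawn are instead more reaction-prone than the rest, as in the termination example above, the all-entrant odds ratio falls below 1 (0.88 for 5 of 100). The two populations can therefore err in opposite directions.

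**Missed days.** The same mixing applies, but the documents give nothing from which to size it.

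**The case against.** The strongest reply is that Aim 2 sets out to compare stages and does so. The synopsis defines the stages, OIT as a regimen includes build-up, and no passage calls the contrast flour against food at equal dose. The sentence in section 1.B can also be read as comparison by future research. All of this stands: the stage estimate is a valid description and should be kept. What it leaves unanswered is the transition to food, which section 1.B presents as a gap in knowledge and for which no other analysis is planned.

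A second reply is that the flexible parts of the plan could cover this. The sensitivity analyses in section 10.B are described as perturbations of methods and assumptions, with extreme values as the example; they do not name a different comparison. The exploratory risk-factor models could include phase, but none is specified. Daily records would allow a later split, but it would then be chosen with the data in view.

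A third reply is that a maintenance contrast is itself biased and imprecise. That is correct, and it is why two populations are proposed with the bias of each stated.

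A reader might infer that the plan will make food look safer than it is. The documents do not support that. They give no AE rates by phase, so the direction is unknown, and the reversal in the illustration needs build-up to have about 1.8 to 2.3 times the maintenance rate when food is truly 1.5 times worse.

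**Conclusion.** The point holds as a cheap improvement. The planned Aim 2 contrast is sound for describing the two stages, but not for comparing flour with food, because build-up makes up about 38% to 62% of flour time and none of the food stage. Termination and visit frequency differ between the stages as well. The share follows from the documents and depends on step length and on whether the 6-month limit binds. The size and direction of the distortion rest on assumed rates and on an assumed true ratio of 1.5. A reader might go further and call the Aim 2 analysis invalid; its stated aim does not support that.

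**What to change.** Keep the stage comparison. In section 10.B, Aim 2, add:

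1. OIT AE rates and proportion of missed days, reported separately for escalation with build-up and for 300 mg maintenance.
2. A pre-specified estimate with 95% CI of AE rate and proportion of missed days for food against 300 mg flour maintenance. Use a log-linear count model with days as offset and participant-clustered variance. Include all participants who enter 300 mg maintenance, and report beside it the within-participant estimate among those who switch.
3. A statement of limits. The first estimate can favour food, because those withdrawn in maintenance never contribute food time. The second can disfavour food, because it drops those who did badly in maintenance. Food always follows flour, so time on treatment stays mixed with product in both.

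A look at the first 14 days on food is optional and descriptive only.

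**Cost.** Wording only, using compliance sheets already kept, with no new visit or call. Precision is modest. Assume 50 switchers, 0.01 AEs per maintenance day and a true ratio of 1.5. Expected events are 50 × 182 × 0.01 × 1.5 = 136.5 on food and 50 × 91 × 0.01 = 45.5 in maintenance. The interval exp(ln 1.5 ± 1.96 × √(φ(1/136.5 + 1/45.5))) is 1.07 to 2.10 at φ = 1 and 0.93 to 2.41 with doubled variance (φ = 2). A 14-day window with a true ratio of 2 has 50 × 14 × 0.01 × 2 = 14 events and gives 0.86 to 4.67 at φ = 2. Ascertainment would be similar but not identical: food has a phone call at 9 months and sheets returned at 12 months, while maintenance ends with a visit after about three months.

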3. OBJECTIVES AND OUTCOME MEASURES

A. OBJECTIVES

1. The primary objective of this study is to place patients who have been involved in peanut immunotherapy research on salvage therapy while investigating safety and compliance of oral immunotherapy and food equivalent therapy in these patients.
2. The secondary objectives include:
 - a. Investigation of incidence of gastrointestinal adverse event, drop outs, and Epipen use.
 - b. Investigation of the compliance of participation with peanut OIT and peanut food equivalent

B. OUTCOME MEASURES

1. Primary Outcomes
 - Overall incidence rate of adverse events (including both AEs and SAEs)

during the entire 2-stage treatment sequence (OIT followed by peanut containing food equivalent)

- Overall number of days of treatment missed during the entire 2-stage treatment sequence

2. Secondary Outcomes

- Stage-specific incidence rate of all adverse events
- Days of treatment missed during each stage of treatment.
- Overall incidence rate of gastrointestinal AEs during the entire 2-stage treatment sequence.
- Overall incidence rate of Epipen use
- Overall incidence rate of drop-outs due to gastrointestinal AEs during the entire 2-stage treatment sequence.

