10. STATISTICAL CONSIDERATIONS AND ANALYSIS STRATEGY

A. INTERIM AND FINAL ANALYSES

An interim analysis will be performed when at least 50 patients have finished their peanut OIT treatment phase and at least 25 patients finished 6 months of food equivalent treatment phase.

The interim analysis and the final analyses will include all subjects in the study who provided complete follow up information regarding their

compliance and adverse events, and will also include those who dropped out or were withdrawn from the study before its completion.

The final analyses will be performed when all subjects have completed the study.

B. PLANS FOR EACH SPECIFIC AIM

Aim 1. Investigate the safety and compliance in the 2-stage protocol in subjects who either (a) have previously developed desensitization and then subsequently lost this protection due to a period of time off of therapy, or (b) have previously endured an extended time on placebo therapy.

We will rely on the following methods to accomplish Aim 1:

1. Our primary analysis will focus on estimates of incidence rates of adverse events and the proportion of days of treatment missed during the treatment protocol.
2. Our secondary analyses will include estimation of
 - the overall incidence rate of gastrointestinal AEs during the entire 2-stage treatment sequence.
 - the overall incidence rate of Epipen use
 - the overall incidence rate of drop-outs due to gastrointestinal AEs during the entire 2-stage treatment sequence.
3. Exploratory analyses will be used to investigate potential candidate risk factors for AEs (using logistic regression models) and causes of missed treatment days (using generalized log-linear models for counts of days).
4. Descriptive tabular and graphical methods will be used to visualize the data and examine the relationships among the measures of interest using graphical and descriptive methods.

All statistical estimates will be tabulated with the corresponding 95% confidence intervals (CI). Interpretation of these CIs will be an integral part of the analyses. For Aim 1 (and for all the aims) sensitivity analyses will be performed to evaluate the robustness of the main results to reasonable perturbations of the choices of statistical methods and statistical assumptions used. For example, the influence of any extreme or questionable data value will be explored. Results of the sensitivity analyses will only be used to guide our level of confidence in the main results.

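### Aim 2 compares stage-specific AE incidence rates by logistic regression without giving the rate a unit, a time-at-risk denominator or a within-participant method

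*Combined protocol and SAP*

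**What the plan says.** Section 3.B lists as a secondary outcome the "Stage-specific incidence rate of all adverse events". Section 10.B, Aim 2, item 1 takes this up: "Our main analyses will focus on stage-specific estimates of incidence rates of adverse events and the proportion of days of treatment missed". The model follows at once: "Comparisons of the two stages will rely on logistic regression models for rates, and generalized log-linear models for counts of days".

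Item 2 repeats the arrangement for the secondary outcomes. Logistic regression again serves for rates, which include GI AEs, and the only count model is "generalized log-linear models for counts of Epipen usages". The same item also speaks of "stage-specific incidence rates of drop-outs due to gastrointestinal AEs", although a participant can drop out only once.

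The stage contrast is described as "estimates of differences between stage-specific parameters (e.g., odds ratios, or rate differences"), each with a 95% confidence interval (CI). No hypothesis tests are planned.

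On who is analysed, section 10.A says the analyses "will also include those who dropped out or were withdrawn from the study before its completion".

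Neither section 3.B nor section 10 says whether an AE rate is per participant, per day, per dose or per person-time. Neither gives a rule for repeat events or a method for the correlation between two stages supplied by the same people.

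**The concern.** Section 8.A counts any new event or worsening during the study as an AE, related or not, so one participant can have several in a stage. An incidence rate of such events is naturally events over time at risk. Logistic regression models a binary outcome, so it can be applied here in two ways.

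- **Per participant (any AE in the stage, yes or no).** Repeat events and time at risk drop out. Time at risk can differ between stages: drop-outs stay in the analysis, severe symptoms in build-up end participation (5.D.3), and the switch to food depends on an investigator assessment (5.D.4). Someone who leaves during OIT adds a short, partly observed record to Stage 1 and nothing to Stage 2.
- **Per day (AE on that day, yes or no).** Time at risk is handled, but the days come from the same people. With no method named for that, the interval may be too narrow if a participant's tendency to have AEs differs between stages.

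Aim 2 is read entirely from point estimates and intervals. A per-participant analysis could show a stage difference where daily rates are equal, and a per-day analysis could overstate precision.

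**Working it through.** The plan states no AE rate, precision or power, and section 10.C sets the sample size (up to 100) on ethical grounds. There is therefore no planned figure to reproduce. AE rates, heterogeneity and leaving rates below are assumptions. All ratios are food stage versus OIT stage.

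**1. Formula for the per-participant reading.** Let mu be the mean number of AEs per participant in a stage and v the between-participant variance of the rate (gamma). Then P(any AE) = 1 − exp(−mu) if v = 0, and 1 − (1 + v·mu)^(−1/v) otherwise. The OR is the food odds divided by the OIT odds.

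**2. Equal time, everyone completes.** With equal rates the two probabilities are the same and the OR is 1.00. Now let the true rate ratio be 0.5. Example with v = 0 and means of 2 and 1: odds are e² − 1 = 6.389 and e − 1 = 1.718, so the OR is 1.718/6.389 = 0.27.

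| v | OIT mean 0.5 | OIT mean 2 | OIT mean 4 |
|---|---|---|---|
| 0 | 0.44 | 0.27 | 0.12 |
| 0.5 | 0.47 | 0.42 | 0.38 |
| 1 | 0.50 | 0.50 | 0.50 |
| 2 | 0.54 | 0.59 | 0.62 |

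The same halving of the rate gives an OR anywhere from 0.12 to 0.62. The two agree exactly at v = 1.

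**3. Equal daily rates, some leave OIT at random.** Take 2 AEs per full stage, v = 0.5, and a leaving time uniform over OIT.
- Full stage: P = 1 − (1 + 1)^(−2) = 0.75, odds 3.
- Leaver: P = 1 − ∫₀¹(1 + u)^(−2) du = 0.50.
- With 20% leaving, OIT P = 0.8 × 0.75 + 0.2 × 0.50 = 0.70, odds 2.333, OR = 3/2.333 = 1.29.
- With 10%, OIT P = 0.725, odds 2.636, OR 1.14. With 5%, OIT P = 0.7375, odds 2.810, OR 1.07.

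Simulation with n = 100, log-normal variation of variance 0.5 or 1 and between-stage correlation 1 or 0.5 gives the same picture:

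| Leaving OIT | Any-AE OR | Coverage of 1, ordinary logistic 95% CI |
|---|---|---|
| 5% | 1.05 to 1.08 | 96 to 97% |
| 10% | 1.12 to 1.16 | 94 to 96% |
| 20% | 1.24 to 1.33 | 88 to 92% |

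A person-time rate ratio with participant-clustered variance gives 1.00, with coverage of about 94 to 95%.

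**4. Per-day reading.** For AEs on 1% versus 2% of days, the OR is (0.01/0.99)/(0.02/0.98) = 0.495, against a rate ratio of 0.5. The estimate is sound. In the 20% leaving case, an unclustered interval covers 94 to 95% of the time if each participant's AE tendency is the same in both stages, but 82 to 88% if the between-stage correlation is 0.5.

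**5. Leaving triggered by a Stage 1 AE.** Assume each OIT AE ends participation with probability 0.12, so that 19 to 21% leave.
- Equal rates: the person-time ratio is about 0.91 to 1.02, with coverage 88 to 95%. The any-AE OR is 0.86 to 0.95, with coverage no worse.
- True ratio 0.5: the person-time ratio is about 0.46 to 0.51 (coverage 89 to 94%) and the any-AE OR about 0.35 to 0.40 (coverage of 0.5: 82 to 90%).

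**The case against.** The strongest reply is that the plan intends an incidence proportion. It uses log-linear models where it wants counts, logistic regression for rates, and the word rate even for once-only drop-outs. On that reading an OR is a legitimate summary, rate differences are also listed, and sensitivity analyses on the choice of method are promised. This has force: the plan is ambiguous rather than plainly wrong. But a proportion of participants with any AE is still not comparable between stages when time at risk differs. The rate difference is only an example, has no stated denominator, and does not come directly from a logistic model. The sensitivity analyses do not replace the main model; under Aim 1, for all aims, the plan says: "Results of the sensitivity analyses will only be used to guide our level of confidence in the main results".

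A reader might infer more than the documents support, in four ways.

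- **That the plan treats days as independent.** It does not say so. It is silent on within-participant correlation, and the interval is about right if AE tendency is stable between stages.
- **That the schedule itself makes the stages grossly unequal.** An OIT stage of 259 days (8 × 21 + 91, taking 3 months as 91 days) needs every build-up visit at the end of its window. It also exceeds the 16-week build-up limit in 5.C and the 6-month limit in 7.E. At 179 or 182 days of OIT against 182 of food, with 2 AEs per 182 days, equal rates give ORs of only 1.00 to 1.04.
- **That a person-time model cures everything.** Step 5 shows that it is not clearly better when rates are equal and leaving is triggered by AEs.
- **That the primary results are undermined.** The overall AE rate shares the missing unit, but the stage model is not applied to it.

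**Conclusion.** The concern holds as a model mismatch combined with a specification gap, and should be fixed before analysis. The named model fits recurrent events over possibly unequal time poorly, and the plan does not say which of two different analyses it means.

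The size is conditional. It is negligible for equal rates when both stages last about 6 months and all complete. It is modest at 5 to 10% random leaving, where ordinary intervals still cover adequately. It is material at 20%, with ORs of 1.24 to 1.33 under no difference. When the rates truly differ, the per-participant OR can misstate the rate ratio even with complete follow-up, except when AEs are rare or v is near 1. On the per-day reading only the interval is in doubt.

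The consequence is confined to the modelled stage contrast, which is secondary, in a single-arm study without hypothesis tests.

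**What to change.** In section 10.B, Aim 2:

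1. Define the AE and GI-AE rate in each stage as events divided by person-time at risk in that stage, with repeat events counted.
2. For the stage comparison of AEs and GI AEs, replace logistic regression with a Poisson or negative-binomial log-linear model. Use log person-days at risk as offset and robust variance clustered on participant. Report the rate ratio and the rate difference, each with a 95% CI.
3. Keep logistic regression for drop-out due to GI AEs, which happens once.
4. State that leaving triggered by Stage 1 AEs can still bias the stage contrast, so that the result is read with that limit.

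The cost is SAP wording and a little more analysis work in standard software. No new data are needed: the daily diary (5.G) and compliance sheets (6.F) already record doses and reactions. Separately, the OIT durations in 5.C, 5.D.3 and 7.E conflict and must be reconciled.
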